5. TREATMENT PLAN

5.1 Enrollment and Screening Process

Prior to any study-required tests, subjects must first provide written informed consent to participate in this study. All lab tests should be completed within 3 weeks prior to registration: Complete history, physical examination, and evaluation of ECOG Performance Status. CBC; serum chemistry tests to include alkaline phosphatase, creatinine, electrolytes, AST (SGOT), and total bilirubin. All radiographic studies (CT with contrast or MRI of the head and neck region, CT of chest or chest x-ray) should be completed within: a) Cohort 1: 6 weeks prior to registration, OR b) Cohort 2: within 8 weeks prior to registration.

5.2 Cisplatin Administration

Treatment will be administered on an inpatient or outpatient basis. Reported adverse events and potential risks are described in Section 7. Appropriate dose modifications are described in Section 6. No investigational or commercial agents or therapies other than those described below may be administered with the intent to treat the patient's malignancy.

5.2.1 Planned Treatment

Treatment will consist of standard of care radiation therapy to the primary tumor of the head and neck and involved nodal metastasis and draining nodal basin, as determined by treating radiation oncologist. Patients will be randomized to receive cisplatin at 100 mg/m² every 3 weeks (3 doses) during radiation versus cisplatin at 40 mg/m² once weekly (7 doses) during radiation. This will provide similar cumulative doses of cisplatin in all arms of the study.

Cisplatin Arm	Maximum Cumulative Dose
Every 3 weeks	300 mg/m ²
Weekly	280 mg/m ²

According to a recent review, total doses above 200 mg/m² during radiation lead to higher overall survival [17], and every attempt will be made to reach at least 200 mg/m². Because of the significant differences in response to therapy in oropharyngeal carcinoma (OPC) due to human papilloma virus (HPV) infection, HPV status will be recorded at baseline and adjusted during final analyses where appropriate.

Patients will first be designated by the enrolling CRA, in conjunction with the enrolling physician, as either: a) Cohort 1 (locally advanced non-nasopharyngeal SCCHN that is unresectable) OR b) Cohort 2 (resected and at high risk of recurrence with at least one of the following criteria: extracapsular nodal extension, or invasive cancer at the primary tumor resection margin (positive margin), lymphovascular invasion or perineural invasion, pT3 or pT4 primary, or the presence of multilevel nodal disease. Subjects will then be randomized to receive either Arm 1 or Arm 2 cisplatin as below.

Radiation and Cisplatin will be given concurrently and should start on the same day, \pm 1 day. Radiation will continue without interruption whenever possible. Radiation delays or interruptions will be the decision of the treating radiation oncologist, as outlined in section 5.3.

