3. PATIENT SELECTION

3.1 Eligibility Criteria

- 3.1.1 Patients must have pathologically (histologically or cytologically) proven diagnosis of head and neck squamous cell carcinoma (HNSCC) involving the oral cavity, oropharynx, larynx, hypopharynx, paranasal sinuses or unknown primary squamous carcinoma limited to the head and neck region;

- Cohort 1: Unresectable locally advanced non-nasopharyngeal SCCHN without evidence of distant metastases
- Cohort 2: Patients with non-nasopharyngeal SCCHN who have undergone gross total surgical resection within 63 days prior to registration. Patients must have at least 1 of the following high-risk pathologic features: extracapsular nodal extension, invasive cancer at the primary tumor resection margin (positive margin), lymphovascular invasion or perineural invasion, or the presence of multilevel nodal disease. Patients must be without evidence of distant metastases.

3.1.2 Women of childbearing potential and male participants who are sexually active must agree to use a medically effective means of birth control.

3.1.3 Cohort 1: Patients in Cohort 1 must have either (a) measurable disease, defined as at least one lesion that can be accurately measured in at least one dimension (longest diameter to be recorded for non-nodal lesions and short axis for nodal lesions) as ≥ 20 mm (≥ 2 cm) with conventional techniques or as ≥ 10 mm (≥ 1 cm) for non-nodal lesions, and > 15 mm (> 1.5 cm) for nodal lesions with spiral CT scan, MRI, or calipers by clinical exam or (b) evaluable disease based on evaluable non-target lesions (< 1.5 cm - > 1.0 cm) as specified in protocol section 11.1.1. See Section 11 for the evaluation of measurable disease.

Cohort 2: Subjects in the post-operative setting (Cohort 2) are not required to have measurable disease and response rate will not be assessed in cohort 2.

Date of resection: _____

3.1.4 Patients may have a history of prior head and neck malignancy, but must be able to tolerate full dose radiation and chemotherapy for the current head and neck cancer, as determined by the treating oncologist.

3.1.5 Age ≥ 18 years.

3.1.6 ECOG performance status 0, 1 or 2 (see Appendix A).

3.1.7 Life expectancy of greater than 12 weeks.

3.1.8 Patients must have normal organ and marrow function assessed within 14 days prior to registration as defined below:

- absolute neutrophil count $\geq 1,000/\text{mcL}$
- platelets $\geq 100,000/\text{mcL}$
- creatinine within normal institutional limits

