13.3 Stratification Factors

13.3.1 Randomization will be stratified by type of SCCHN: Cohort (1) is unresectable and Cohort (2) is resected and at high risk of recurrence as defined by the presence of one of the following criteria:

- extracapsular nodal extension
- invasive cancer at the primary tumor resection margin (positive margin)
- lymphovascular invasion
- perineural invasion
- pT3 or pT4 primary
- presence of multilevel nodal disease

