13.4 Analysis Plan

Following study completion, the percentage of subjects experiencing cisplatin-related actual toxicities in each group will be estimated along with exact 95% binomial confidence intervals. A Fisher's exact test will also be employed to test for differences between toxicity rates.

For all toxicity outcomes, incidence tables will be generated to summarize incidence of patients reporting at least one episode of each adverse event, incidence of adverse events causing withdrawals and incidence of serious adverse events. Listing of adverse events by patients will include the time to onset, the duration of each event, the severity of each event, and the relationship of the event to study therapy, whether it was a serious event, and whether it caused withdrawal.

All correlative and secondary endpoints are exploratory in nature and will be primarily descriptive; however, response and 2-year local control rates will be estimated with corresponding 95% confidence intervals and assessed for differences using Fisher's exact tests. PFS and OS will be displayed using Kaplan-Meier curves with estimated median times, and differences will be assessed using log rank tests. Repeated measures mixed models will be utilized to assess for differences in quality of life and correlative outcomes over time and between randomization groups.

In addition to those outlined above, subgroup analyses will also be run for each stratification cohort as numbers allow.

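### HPV adjustment is promised where appropriate, but the analysis plan gives the response, local control, PFS and OS tests no HPV term and does not use the cohort stratum in them

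*Combined protocol and SAP*

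**What the plan says.** Section 5.2.1 gives both a reason and a commitment. The reason is "Because of the significant differences in response to therapy in oropharyngeal carcinoma (OPC) due to human papilloma virus (HPV) infection". The commitment is that "HPV status will be recorded at baseline and adjusted during final analyses where appropriate". No endpoint, model or HPV definition follows.

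HPV status will vary between patients, because section 3.1 admits disease "involving the oral cavity, oropharynx, larynx, hypopharynx, paranasal sinuses or unknown primary squamous carcinoma". Section 2.1 also lists HPV-driven cancer among the features that predict sensitivity to cisplatin.

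Section 13.3 states that "Randomization will be stratified by type of SCCHN", meaning unresectable or resected high-risk disease. HPV is not a randomisation factor.

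Section 13.4 sets out the analyses:
- Primary toxicity: a Fisher's "exact test will also be employed to test for differences between toxicity rates".
- Efficacy rates: "response and 2-year local control rates will be estimated with corresponding 95% confidence intervals and assessed for differences using" Fisher's exact tests.
- PFS and OS: Kaplan-Meier curves, and "differences will be assessed using log rank tests".
- Quality of life and correlatives: "Repeated measures mixed models will be utilized to assess for differences in quality of life and correlative outcomes over time and between randomization groups".

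Cohort appears in 13.4 only as a basis for subgroup analyses. The section also describes all secondary and correlative endpoints as exploratory and mainly descriptive.

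**The concern.** Fisher's exact test takes no covariate, and an ordinary log-rank test has no strata. Someone carrying out 13.4 alone would produce unadjusted efficacy comparisons. Someone carrying out 5.2.1 would have to choose the endpoints, the model, the HPV categories, the handling of unknown status and the result that leads. The trial is unblinded, so those choices could be made by people who have already seen outcomes by arm.

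The efficacy comparison matters to how the trial will be read. Section 2.3 describes the study as designed partly to compare efficacy between the schedules, and section 2.5 hypothesises comparable local control with less toxicity. With about 40 patients per arm, a chance imbalance in a strong prognostic factor could mimic or hide a difference. A reader could not then tell whether the adjusted or the unadjusted result was the planned one.

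**Working it through.** **1. The plan's own figure.** Section 13.2 gives 36 per arm, toxicity 80% v 50%, Fisher's exact test, one-sided 0.05, 80% power. Exact enumeration gives 80.9% at 36 per arm and 79.1% at 35. Recruitment: 72 / (1 − 0.10) = 80. The sample size reproduces, for an unadjusted test of toxicity. It says nothing about efficacy or HPV.

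**2. Commitment against method.**

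| Endpoint | Method in 13.4 | HPV | Cohort |
|---|---|---|---|
| Response (Cohort 1 only) | Fisher's exact | none | not applicable |
| 2-year local control | Fisher's exact | none | not used in test |
| PFS, OS | log-rank | none | not used in test |
| Quality of life, correlatives | mixed models | possible, none named | none named |

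**3. Chance of HPV imbalance.** The documents give no HPV prevalence, so it is assumed. Take the HPV-positive counts in the two arms as independent Binomial(40, p). At p = 0.40 the standard deviation of the difference in proportions is √(2 × 0.4 × 0.6 / 40) = 0.110. Exact results:
- A difference of at least 10 points (4 patients of 40): 42%.
- A difference of at least 20 points (8 patients of 40): 9%.

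At 40 per arm with p = 0.20, these are 33% and 4%; with p = 0.50, 43% and 9%. At 36 per arm with p from 0.20 to 0.70, they run from 30% to 41% and from 3% to 8%. Stratifying by cohort alters this only to the extent that HPV status is related to cohort.

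**4. From imbalance to a shifted comparison.** Shift in the arm difference ≈ imbalance × outcome gap by HPV status.
- A 15-point imbalance with an assumed gap of 15 to 35 points: 0.15 × 0.15 = 2.3 points, up to 0.15 × 0.35 = 5.3 points.
- A 20-point imbalance with exponential times, a 24-month baseline median and hazard multipliers of 0.35 (HPV-positive) and 1.3 (others), all assumed: 2-year event rates are 1 − 0.5^0.35 = 0.215 and 1 − 0.5^1.3 = 0.594. The shift is 0.20 × 0.378 = 7.6 points.
- The same imbalance with a milder HPV hazard ratio of 0.6: 1 − 0.5^0.6 = 0.340 against 0.500. The shift is 0.20 × 0.160 = 3.2 points.

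Simulating no true arm difference with a 20-point imbalance fixed, the unadjusted two-sided 5% log-rank test rejects about 9% of the time under the stronger HPV effect and about 6% under the milder one. The HPV-stratified test stays near 5% in both.

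**5. Averaged over randomisations.** With the imbalance left to chance and no arm difference, both tests reject about 5% of the time. Power for an assumed arm hazard ratio of 0.5 over 24 months:

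| Assumptions | Unadjusted | Stratified by HPV |
|---|---|---|
| 80 patients, multipliers 0.35 and 1.3, 40% HPV-positive | 40% | 44% |
| 72 patients, HPV hazard ratio 0.6 to 0.25, 30% or 50% HPV-positive | 29–40% | 31–41% |

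Stratifying by HPV and a non-prognostic cohort together (80 patients, same multipliers, baseline median 24 or 36 months) gives 43% or 33%, against 40% or 33% unadjusted, on 21 to 28 events. Across these runs the gain is about 0 to 4 points.

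**The case against.** The closing qualifier in 5.2.1 makes the commitment conditional, and naming simple tests in 13.4 does not forbid a further adjusted analysis. A reader might infer that the two sections flatly contradict each other, or that every planned analysis excludes HPV. The text supports neither: the adjustment is unspecified rather than ruled out, and the mixed models could carry an HPV term although none is named.

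The affected endpoints are exploratory by the plan's own statement. HPV is raised because of response to therapy, not toxicity, so the primary test and sample size stand. Leaving HPV out of the randomisation strata is a permissible choice with 80 patients and one stratum already in use.

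The statistical gain is also modest. Power for efficacy is poor with or without adjustment, and every HPV figure above is an assumption.

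All of that stands. It limits the point without removing it. Exploratory status does not settle which result leads once between-arm tests are planned and reported, and the qualifier is what leaves that choice open until after the data are seen.

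**Conclusion.** The point holds as a gap in specification affecting response, 2-year local control, PFS and OS. The plan gives a reason to adjust for HPV and promises to do so where appropriate, but its named tests do not do it and also leave the randomisation stratum unused.

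A reader might infer that the unadjusted tests are invalid. They are not: randomisation protects their type I error on average. Nor is lost power the main argument. The case rests on two things: a chance imbalance in the trial actually run, and an adjustment chosen after open-label data are visible. An imbalance of 20 points is uncommon (about 9% at 40% prevalence) but could move a 2-year event-rate difference by roughly 3 to 8 points under the HPV effects assumed. An imbalance of 10 points is common (42%) and matters less. These sizes depend on assumed HPV prevalence and effects; the textual gap does not.

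**What to change.** In section 13.4:
- Stratify the PFS and OS log-rank tests by cohort and HPV category (HPV-positive oropharynx v all others), with a stated rule for unknown status.
- Report hazard ratios from a Cox model with the same two factors.
- Analyse 2-year local control with the same factors, by Cochran-Mantel-Haenszel or logistic regression.
- For response, which is assessed in Cohort 1 only, use HPV category alone.
- Collapse sparse strata by a rule fixed in advance and applied without reference to arm.
- State that the adjusted results lead, and keep the unadjusted tests as supportive.

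Add HPV status to the baseline items in sections 5.1 and 10. Neither lists it now, although 5.2.1 says it will be recorded.

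The cost is a short amendment to 13.4, two baseline entries with an HPV definition, and a little more analysis work. The downside is possible sparse strata, since four cells share few events. Treatment, sample size and the primary toxicity analysis do not change.

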5.2.2 Cisplatin Dosing

Use the actual body weight as long as the BSA is ≤ 2.3 . If the BSA is > 2.3 , recalculate using the adjusted body weight, and use the recalculated BSA to determine the dose with no cap.

Estimate Ideal body weight in (kg)

Males: IBW = 50 kg + 2.3 kg for each inch over 5 feet

Females: IBW = 45.5 kg + 2.3 kg for each inch over 5 feet

Adjusted body weight

$$AjBW = IBW + 0.4(ABW - IBW)$$

Arm 1 – Conventional fractionation plus every 3-week cisplatin

Patients will receive cisplatin (100 mg/m²) administered intravenously over 1 hour on days 1, 22, and 43 of the treatment course, relative to the initiation of radiation.

Arm 2 – Conventional fractionation plus weekly cisplatin

Patients will receive cisplatin (40 mg/m²) administered intravenously over 1 hour on days 1, 8, 15, 22, 29, 36, and 43 of the treatment course, relative to the initiation of radiation.

Premedication: Arms 1 & 2

Suggested premedication: include aprepitant (intravenous or oral), ondansetron, dexamethasone and either promethazine or prochlorperazine, per institutional standard. This trial endorses the NCCN guidelines for anti-emetic prophylaxis.

Pre- and Post-hydration: Arms 1 & 2

Patients must receive vigorous hydration and diuresis. A suggested regimen is: pre-hydration with a 1 liter of normal saline with electrolyte supplementation (e.g. potassium, magnesium) per standard of care, over 2 hours i.v. immediately prior to cisplatin. Then cisplatin 100 mg/m² in 500 ml normal saline is administered over 1 hour. Following cisplatin infusion, an additional 1 liter of normal saline with electrolyte supplementation (e.g. potassium, magnesium) per standard of care, given post-hydration over 2 hours.

Please see Section 6.0 for all dose modifications of cisplatin.

5.3 **Radiation Therapy**

All radiation therapy is considered standard of care, and toxicities and dose modifications will be made by the treating physician based on institutional standards. The guidelines below are recommended practice but may be modified at the discretion of the treating radiation oncologist.

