10. STUDY CALENDAR

Baseline evaluations are to be conducted as follows:

- Within 3 weeks prior to registration: Complete history, physical examination, and evaluation of ECOG Performance Status, CBC; serum chemistry tests to include alkaline phosphatase, creatinine, electrolytes, AST (SGOT), and total bilirubin.
- All radiographic studies should be completed within:
 - Cohort 1: 6 weeks prior to registration
 - Cohort 2: 8 weeks prior to registration
- In the event that the patient's condition is deteriorating, laboratory evaluations should be repeated within 48 hours prior to initiation of the next cycle of therapy.

Pre-Study	Wk 1	Wk 2	Wk 3	Wk 4	Wk 5	Wk 6	Wk 7	Post Treatment Follow up	Long term Follow up ^b
Cisplatin Arm 1	A			A			A		
Cisplatin Arm 2	B	B	B	B	B	B	B		
Informed consent	X								
Demographics, medical history	X								
Concurrent meds		X ⁱ							
Physical exam	X	X		X			X	X	X ^h
Pulse, blood pressure	X	X		X			X	X	
Height	X								
Weight ^a	X	X	X ^a	X ^a	X	X ^a	X ^a	X	
Performance status	X	X						X	
CBC w/diff, plts ^a	X	X	X ^a	X ^a	X	X ^a	X ^a	X	X
Serum basic chemistry ^b			X ^a	X ^a		X ^a	X ^a		
Serum comprehensive chemistry ^c	X	X		X			X	X	
Adverse event evaluation		X-----							X
Tumor measurements	X ^d							X ^e	X ^e
B-HCG	X ^f								
Correlative studies		X							
FACTHN and FACT-COG ^g	X ^g						X ^g	X ^g	

A: Arm 1: Cisplatin 100 mg/m² every 3 weeks for 3 total doses

B: Arm 2: Cisplatin 40 mg/m² every week for 7 total doses

a: Every 3 weeks for Arm 1 during radiation, weekly for Arm 2 during radiation, and then as scheduled.

b: Weeks 2,3,5, 6 of Arm 2 only: creatinine, glucose, potassium, sodium.

c: Every three weeks for both arms: Albumin, alkaline phosphatase, total bilirubin, calcium, creatinine, potassium, SGOT [AST], SGPT [ALT], sodium.

- d: Baseline scans can include either: 1) CT with contrast or MRI of the head and neck region, CT of chest or chest x-ray. Response assessment should include assessment of all sites of disease and use the same imaging method as was used at baseline.
- e: Restaging scans must be repeated after the end of protocol treatment within 8 weeks of completion of radiation. Thereafter, scans of the head and neck will be repeated as clinically indicated, but at a minimum of every 6 months (± 6 weeks) for the first two years. Following this, all scans are at the treating physician's discretion.
- f: Serum pregnancy test (women of childbearing potential).

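### The suggested hydration and infusion text in 5.2.2 is headed for both arms but names one cisplatin dose, 100 mg/m², which contradicts the 40 mg/m² stated for Arm 2

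*Combined protocol and SAP*

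**What the plan says.** Section 5.2.1 sets out the randomised comparison as "cisplatin at 100 mg/m² every 3 weeks (3 doses) during radiation versus cisplatin at 40 mg/m² once weekly (7 doses) during radiation". It adds "This will provide similar cumulative doses of cisplatin in all arms of the study" and tabulates maximum cumulative doses of 300 mg/m² (every 3 weeks) and 280 mg/m² (weekly).

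Section 5.2.2 then gives each arm its own paragraph:

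- Arm 1: "Patients will receive cisplatin (100 mg/m²) administered intravenously over 1 hour on days 1, 22, and 43 of the treatment course".
- Arm 2: "Patients will receive cisplatin (40 mg/m²) administered intravenously over 1 hour on days 1, 8, 15, 22, 29, 36, and 43".

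A later paragraph of 5.2.2 is headed "Pre- and Post-hydration: Arms 1 & 2". It requires hydration and diuresis, then offers an example: "A suggested regimen is: pre-hydration with a 1 liter of normal saline with electrolyte supplementation". Within that example comes the sentence "Then cisplatin 100 mg/m² in 500 ml normal saline is administered over 1 hour", followed by the post-hydration. The paragraph does not mention 40 mg/m² or the assigned arm. The section ends by sending the reader to Section 6 for dose modifications.

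**The concern.** The heading applies the paragraph to both arms, while its only dose figure is the one that the protocol gives for Arm 1. Anyone applying the paragraph to an Arm 2 patient meets two different doses within one section.

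The paragraph also sets out the whole infusion-day sequence: fluid before, drug in a stated volume over a stated time, fluid after. That makes it a natural source for an order template.

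Cisplatin dose and schedule are what the trial randomises, and the primary endpoint (1.1.1 and 13.1) is grade 3-5 cisplatin-related toxicity in the first 90 days. Section 7.1 describes the drug's nephrotoxicity as dose-related and cumulative. If an Arm 2 order were written from this paragraph, the patient could be put at risk, and the toxicity contrast that the trial is built to measure could be distorted.

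**Working it through.** **1. The plan's own cumulative figures.** Formula: dose per administration × number of administrations, using the doses and days in 5.2.2.

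- Arm 1: 100 × 3 = 300 mg/m². This matches the table in 5.2.1.
- Arm 2: 40 × 7 = 280 mg/m². This matches the table in 5.2.1.

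The arm paragraphs and the cumulative table therefore agree with each other.

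**2. Starting dose that each place gives for the weekly arm.**

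| Place | Weekly-arm dose |
|---|---|
| 1.1.2, hypothesis | 40 mg/m² |
| 5.2.1, randomised regimens | 40 mg/m² (maximum 280 mg/m²) |
| 5.2.2, Arm 2 paragraph | 40 mg/m² |
| Section 6, dose level 0 | 40 mg/m² |
| Section 10, calendar note: "B: Arm 2: Cisplatin 40 mg/m² every week for 7 total doses" | 40 mg/m² |
| 5.2.2, hydration paragraph for both arms | 100 mg/m², no arm qualifier |

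**3. Size of the conflict.** Per administration: 100 / 40 = 2.5.

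**4. Whether another passage resolves it.** The administration text in 8.1 repeats the one-hour infusion and the liter of saline before and after, but names no dose. Section 6 deals with modifications only. Its levels are 100, 75 and 50 mg/m² for the every-3-week arm and 40, 30 and 20 mg/m² for the weekly arm. The fixed 100 mg/m² matches one of these six levels, so it does not fit a dose-reduced Arm 1 infusion either. Neither passage removes the conflict.

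**5. Whether a statistical figure depends on it.** Section 13.2 uses toxicity rates of 80% and 50%, 36 patients per arm, a one-sided 0.05 level and Fisher's exact test. Exact power recomputed from those inputs is 0.809, against the stated 80%. Allowing for 10% loss, 72 / 0.90 = 80, as stated. The infusion sentence enters neither calculation.

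**The case against.** The strongest reply is that the paragraph is about hydration and is not where the protocol sets the dose. The sentence sits inside an example put forward as a suggestion, while the arm paragraphs say what patients will receive. The weekly dose is the same in every other place that states it, one of them a few lines earlier under its own Arm 2 heading. The hydration paragraph also has no days, interval or number of doses, so a complete order cannot be written from it alone. A pharmacist checking against the arm paragraph or the calendar would probably notice the mismatch.

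Most of this stands, and it lowers the likelihood of an error. It does not remove the contradiction. Calling the hydration a suggestion does not make the randomised dose optional, and it supplies no figure for Arm 2.

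A reader might also infer a cumulative Arm 2 dose of 700 mg/m² (7 × 100) against the stated maximum of 280 mg/m². The documents do not support that as a regimen. It takes the seven days from the Arm 2 paragraph while ignoring the dose in the same sentence, and it repeats the mistake seven times in the face of the 280 mg/m² maximum, the dose-level table and the calendar. It is a hypothetical literal reading only.

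**Conclusion.** The contradiction is real and stands in the section that governs dosing: one paragraph addressed to both arms, one unqualified figure, and a different figure for Arm 2 in the same section and in 1.1.2, 5.2.1, Section 6 and Section 10. The size that the text directly supports is the 2.5-fold difference per administration.

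The point rests on reading the heading as it is written and assumes nothing about what happened in practice. It would be going too far to say that patients would be harmed or that the primary comparison is compromised: the documents show no dosing error and give no ground for calling one likely. What they support is that the text could lead to one.

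This is an internal inconsistency, not a fault in the design. The randomised comparison, the planned analysis and the sample size in Section 13 are unaffected. Which text is intended is for the sponsor to confirm.

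**What to change.** The sponsor should reconcile the hydration paragraph in 5.2.2 with the arm paragraphs and confirm the intended text. Either of two edits would do: state the dose by arm in the infusion sentence, or remove the number and refer to the assigned-arm paragraphs and to Section 6. The second also deals with dose-reduced infusions. Any order templates already built from the paragraph should be checked against the confirmed text.

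The cost is a one-line protocol correction plus its usual review. No design, sample size or analysis text has to change.
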